When the patient has only non-measurable disease. This circumstance arises in some phase 3 trials when it is not a criterion of study entry to have measurable disease. The same general concepts apply here as noted above, however, in this instance there is no measurable disease assessment to factor into the interpretation of an increase in non-measurable disease burden. Because worsening in non-target disease cannot be easily quantified (by definition: if all lesions

are truly non-measurable) a useful test that can be applied when assessing patients for unequivocal progression is to consider if the increase in overall disease burden based on the change in non-measurable disease is comparable in magnitude to the increase that would be required to declare PD for measurable disease: i.e., an increase in tumor burden representing an additional 73% increase in 'volume' (which is equivalent to a 20% increased diameter in a measurable lesion). Examples include an increase in a pleural effusion from 'trace' to 'large', an increase in lymphangitic disease from localized to widespread, or may be described in protocols as 'sufficient to require a change in therapy'. If 'unequivocal progression' is seen, the patient should be considered to have had overall PD at that point. While it would be ideal to have objective criteria to apply to non-measurable disease, the very nature of that disease makes it impossible to do so, therefore the increase must be substantial.

New lesions

The appearance of new malignant lesions denotes disease progression; therefore, some comments on detection of new lesions are important. There are no specific criteria for the identification of new radiographic lesions; however, the finding of a new lesion should be unequivocal: i.e., not attributable to differences in scanning technique, change in imaging modality or findings thought to represent something other than tumor (for example, some 'new' bone lesions may be simply healing or flare of pre-existing lesions). This is particularly important when the patient's baseline lesions show partial or CR. For example, necrosis of a liver lesion may be reported on a CT scan report as a 'new' cystic lesion, which it is not.

A lesion identified on a follow-up study in an anatomical location that was not scanned at baseline is considered a new lesion and will indicate disease progression. An example of this is the patient who has visceral disease at baseline and while on study has a CT scan or MRI brain ordered which reveals metastases. The patient's brain metastases are considered to be evidence of PD even if he/she did not have brain imaging at baseline.

If a new lesion is equivocal, for example because of its small size, continued therapy and follow-up evaluation will clarify if it represents truly new disease. If repeat scans confirm there is definitely a new lesion, then progression should be declared using the date of the initial scan.

While FDG-PET response assessments need additional study, it is sometimes reasonable to incorporate the use of FDG-PET scanning to complement CT scanning in assessment of progression (particularly possible 'new' disease). New lesions on the basis of FDG-PET imaging can be identified according to the following algorithm:

Negative FDG-PET at baseline, with a positive FDG-PET (a 'positive' FDG-PET scan lesion means one which is FDG avid with an uptake greater than twice that of the surrounding tissue on the attenuation corrected image) at follow-up is a sign of PD based on a new lesion.

No FDG-PET at baseline and a positive FDG-PET at follow-up:

If the positive FDG-PET at follow-up corresponds to a new site of disease confirmed by CT scan, this is PD.

If the positive FDG-PET at follow-up is not confirmed as a new site of disease on CT scan, additional follow-up CT scans are needed to determine if there is truly progression occurring at that site (if so, the date of PD will be the date of the initial abnormal FDG-PET scan).

If the positive FDG-PET at follow-up corresponds to a pre-existing site of disease on CT scan that is not progressing on the basis of the anatomic images, this is not PD.

Evaluation of Best Overall Response

The best overall response is the best response recorded from the start of the study treatment until the end of treatment taking into account any requirement for confirmation. On occasion a response may not be documented until after the end of therapy so protocols should be clear if post-treatment assessments are to be considered in determination of best overall response. Protocols must specify how any new therapy introduced before progression will affect best response designation. The patient's best overall response assignment will depend on the findings of both target and non-target disease and will also take into consideration the appearance of new lesions. Furthermore, depending on the nature of the study and the protocol requirements, it may also require confirmatory measurement. Specifically, in nonrandomized trials where response is the primary endpoint, confirmation of PR or CR is needed to deem either one the 'best overall response'.

Time point response

It is assumed that at each protocol specified time point, a response assessment occurs. [Table 8](#) below provides a summary of the overall response status calculation at each time point for patients who have measurable disease at baseline.

Table 8: Evaluation of best overall response: patients with measurable and non-measurable disease			
Target Lesions	Non-target Lesions	New Lesions	Overall Response
CR	CR	No	CR
CR	Non-CR/non-PD	No	PR
CR	Not evaluated	No	PR
PR	Non-PD or not evaluated	No	PR
SD	Non-PD or not evaluated	No	SD
Not all evaluated	Non-PD	No	NE
PD	Any	Yes or No	PD
Any	PD	Yes or No	PD
Any	Any	Yes	PD

NE = Not evaluable.

When patients have non-measurable disease only (therefore non-target), the following table is to be used.

Table 9: Evaluation of best overall response: patients with non-measurable disease		
Non-target Lesions	New Lesions	Overall Response
CR	No	CR
Non-CR/non-PD	No	On-CR/non-PD ¹
Not all evaluated	No	NE
Unequivocal PD	Yes or No	PD
Any	Yes	PD

NE = not evaluable.
1 = 'Non-CR/non-PD' is preferred over 'stable disease' for non-target disease since SD is increasingly used as endpoint for assessment of efficacy in some trials so to assign this category when no lesions can be measured is not advised.

Missing assessments and inevaluable designation

When no imaging/measurement is done at all at a particular time point, the patient is not evaluable (NE) at that time point. If only a subset of lesion measurements are made at an assessment, usually the case is also considered NE at that time point, unless a convincing argument can be made that the contribution of the individual missing lesion(s) would not change the assigned time point response. This would be most likely to happen in the case of PD. For example, if a patient had a baseline sum of 50 mm with three measured lesions and at follow-up only two lesions were assessed, but those gave a sum of 80 mm, the patient will have achieved PD status, regardless of the contribution of the missing lesion.

Best overall response: all time points

The best overall response is determined once all the data for the patient is known.

Best response determination in trials where confirmation of CR or PR is not required: Best response in these trials is defined as the best response across all time points (for example, a patient who has SD at first assessment, PR at second assessment, and PD on last assessment has a best overall response of PR). When SD is believed to be best response, it must also meet the protocol specified minimum time from baseline. If the minimum time is not met when SD is otherwise the best time point response, the patient’s best response depends on the subsequent assessments. For example, a patient who has SD at first assessment, PD at second and does not meet minimum duration for SD, will have a best response of PD. The same patient lost to follow-up after the first SD assessment would be considered inevaluable.

Best response determination in trials where confirmation of CR or PR is required: CRs or PRs may be claimed only if the criteria for each are met at a subsequent time point as specified in the protocol (generally 4 weeks later). In this circumstance, the best overall response can be interpreted as in the following table.

Table 10: Best overall response when confirmation of CR and PR is required		
Overall response first time point	Overall response subsequent time point	BEST overall response
CR	CR	CR
CR	PR	SD, PD, OR PR ¹
CR	SD	SD provided minimum criteria for SD duration met, otherwise PD
CR	PD	SD provided minimum criteria for SD duration met, otherwise PD
CR	NE	SD provided minimum criteria for SD duration met, otherwise NE
PR	CR	PR
PR	PR	PR
PR	SD	SD
PR	PD	SD provided minimum criteria for SD duration met, otherwise PD
PR	NE	SD provided minimum criteria for SD duration met, otherwise NE
NE	NE	NE

¹ = If a CR is truly met at first time point, then any disease seen at a subsequent time point, even disease meeting PR criteria relative to baseline, makes the disease PD at that point (since disease must have reappeared after CR). Best response would depend on whether minimum duration for SD was met. However, sometimes ‘CR’ may be claimed when subsequent scans suggest small lesions were likely still present and in fact the patient had PR, not CR at the first time point. Under these circumstances, the original CR should be changed to PR and the best response is PR.

Special notes on response assessment

When nodal disease is included in the sum of target lesions and the nodes decrease to ‘normal’ size (<10 mm), they may still have a measurement reported on scans. This measurement should be recorded even though the nodes are normal in order not to overstate progression should it be based on increase in size of the nodes. As noted earlier, this means that patients with CR may not have a total sum of ‘zero’ on the eCRF.

In trials where confirmation of response is required, repeated ‘NE’ time point assessments may complicate best response determination. The analysis plan for the trial must address how missing data/assessments will be addressed in determination of response and progression. For example, in most trials it is reasonable to consider a patient with time point responses of PRNE-PR as a confirmed response.

Patients with a global deterioration of health status requiring discontinuation of treatment without objective evidence of disease progression at that time should be reported as ‘symptomatic deterioration’. Every effort should be made to document objective progression even after discontinuation of treatment. Symptomatic deterioration is not a descriptor of an objective response: it is a reason for stopping study therapy. The objective response status of such patients is to be determined by evaluation of target and non-target disease as shown in the tables above.

Conditions that define ‘early progression, early death and inevaluability’ are study specific and should be clearly described in each protocol (depending on treatment duration, treatment periodicity).

In some circumstances it may be difficult to distinguish residual disease from normal tissue. When the evaluation of CR depends upon this determination, it is recommended that the residual lesion be investigated (fine needle aspirate/biopsy) before assigning a status of CR. FDG-PET may be used to upgrade a response to a CR in a manner similar to a biopsy in cases where a residual radiographic abnormality is thought to represent fibrosis or scarring. The use of FDG-PET in this circumstance should be prospectively described in the protocol and supported by disease specific medical literature for the indication. However, it must be acknowledged that both approaches may lead to false positive CR due to limitations of FDG-PET and biopsy resolution/sensitivity.

For equivocal findings of progression (e.g., very small and uncertain new lesions; cystic changes or necrosis in existing lesions), treatment may continue until the next scheduled assessment. If at the next scheduled assessment, progression is confirmed, the date of progression should be the earlier date when progression was suspected.

Frequency of tumor re-evaluation

Frequency of tumor re-evaluation while on treatment should be protocol specific and adapted to the type and schedule of treatment. However, in the context of phase 2 studies where the beneficial effect of therapy is not known, follow-up every 6–8 weeks (timed to coincide with the end of a cycle) is reasonable. Smaller or greater time intervals than these could be justified in

specific regimens or circumstances. The protocol should specify which organ sites are to be evaluated at baseline (usually those most likely to be involved with metastatic disease for the tumor type under study) and how often evaluations are repeated.

Normally, all target and non-target sites are evaluated at each assessment. In selected circumstances certain non-target organs may be evaluated less frequently. For example, bone scans (scintigraphy) may need to be repeated only when CR is identified in target disease or when progression in bone is suspected.

After the end of the treatment, the need for repetitive tumor evaluations depends on whether the trial has as a goal the response rate or the time to an event (progression/death). If ‘time to an event’ (e.g., time to progression, disease-free survival, PFS) is the main endpoint of the study, then routine scheduled re-evaluation of protocol specified sites of disease is warranted. In randomized comparative trials in particular, the scheduled assessments should be performed as identified on a calendar schedule (for example: every 6–8 weeks on treatment or every 3–4 months after treatment) and should not be affected by delays in therapy, drug holidays, or any other events that might lead to imbalance in a treatment arm in the timing of disease assessment.

Confirmatory Measurement/Duration of Response

Confirmation

As ORR is not the primary endpoint, confirmation of response is not required.

Duration of Overall Response

The duration of overall response is measured from the time measurement criteria are met for CR or PR (whichever is first recorded) until the first date that recurrent or PD is objectively documented (taking as reference for PD the smallest measurements recorded since the treatment started).

The duration of overall CR is measured from the time measurement criteria are first met for CR until the first date that recurrent disease is objectively documented.

Duration of Stable Disease

SD is measured from the start of the treatment (in randomized trials, from date of randomization) until the criteria for progression are met, taking as reference the smallest measurements recorded since the treatment started (if the baseline sum is the smallest, this is the reference for calculation of PD).

Appendix B
Eastern Cooperative Oncology Group Performance Status Scale

ECOG Performance Status	
0	Fully active, able to carry on all predisease performance without restriction.
1	Restricted in physically strenuous activity but ambulatory and able to carry out work of a light or sedentary nature (e.g., light house work or office work).
2	Ambulatory and capable of all self care but unable to carry out any work activities. Up and about more than 50% of waking hours.
3	Capable of only limited self care; confined to bed or chair more than 50% of waking hours.
4	Completely disabled. Cannot carry on any self care. Totally confined to bed or chair.
5	Dead.

Appendix C

List of concomitant medications that can prolong the QT interval and increase the risk of causing Torsades de Pointes

Medications linked to prolongation of the QT interval and association with Torsade de Pointes can be accessed at: <http://www.crediblemeds.org/everyone/composite-list-all-qtdrugs/?rf=All>

Appendix D
 FACT-B Version 4.0⁵⁷

Below is a list of statements that other people with your illness have said are important. Please circle or mark one number per line to indicate your response as it applies to the past 7 days.

PHYSICAL WELL-BEING		Not at all	A little bit	Some - what	Quite a bit	Very much
GP1	I have a lack of energy.....	0	1	2	3	4
GP2	I have nausea	0	1	2	3	4
GP3	Because of my physical condition, I have trouble meeting the needs of my family	0	1	2	3	4
GP4	I have pain	0	1	2	3	4
GP5	I am bothered by side effects of treatment.....	0	1	2	3	4
GP6	I feel ill.....	0	1	2	3	4
GP7	I am forced to spend time in bed	0	1	2	3	4

SOCIAL/FAMILY WELL-BEING		Not at all	A little bit	Some - what	Quite a bit	Very much
GS1	I feel close to my friends	0	1	2	3	4
GS2	I get emotional support from my family.....	0	1	2	3	4
GS3	I get support from my friends	0	1	2	3	4
GS4	My family has accepted my illness.....	0	1	2	3	4
GS5	I am satisfied with family communication about my illness	0	1	2	3	4
GS6	I feel close to my partner (or the person who is my main support).....	0	1	2	3	4
Q1	Regardless of your current level of sexual activity, please answer the following question. If you prefer not to answer it, please mark this box  and go to the next section.					
GS7	I am satisfied with my sex life.....	0	1	2	3	4

Please circle or mark one number per line to indicate your response as it applies to the past 7 days.

EMOTIONAL WELL-BEING		Not at all	A little bit	Some -what	Quite a bit	Very much
GE1	I feel sad.....	0	1	2	3	4
GE2	I am satisfied with how I am coping with my illness	0	1	2	3	4
GE3	I am losing hope in the fight against my illness.....	0	1	2	3	4
GE4	I feel nervous	0	1	2	3	4
GE5	I worry about dying.....	0	1	2	3	4
GE6	I worry that my condition will get worse.....	0	1	2	3	4

FUNCTIONAL WELL-BEING		Not at all	A little bit	Some - what	Quite a bit	Very much
GF1	I am able to work (include work at home).....	0	1	2	3	4
GF2	My work (include work at home) is fulfilling	0	1	2	3	4
GF3	I am able to enjoy life	0	1	2	3	4
GF4	I have accepted my illness	0	1	2	3	4
GF5	I am sleeping well	0	1	2	3	4
GF6	I am enjoying the things I usually do for fun.....	0	1	2	3	4
GF7	I am content with the quality of my life right now	0	1	2	3	4

Please circle or mark one number per line to indicate your response as it applies to the past 7 days.

ADDITIONAL CONCERNS		Not at all	A little bit	Some -what	Quite a bit	Very much
B1	I have been short of breath.....	0	1	2	3	4
B2	I am self-conscious about the way I dress	0	1	2	3	4
B3	One or both of my arms are swollen or tender	0	1	2	3	4
B4	I feel sexually attractive.....	0	1	2	3	4
B5	I am bothered by hair loss.....	0	1	2	3	4
B6	I worry that other members of my family might someday get the same illness I have	0	1	2	3	4
B7	I worry about the effect of stress on my illness	0	1	2	3	4
B8	I am bothered by a change in weight	0	1	2	3	4
B9	I am able to feel like a woman.....	0	1	2	3	4
P2	I have certain parts of my body where I experience pain.....	0	1	2	3	4

Appendix E.
Inhibitors and Inducers of CYP2C8 and CYP3A4

CYP Enzyme	Strong Inhibitor (Contraindicated)	Moderate Inhibitor (Use with Caution)
CYP2C8	gemfibrozil	teriflunomide
CYP3A4	boceprevir clarithromycin conivaptan grapefruit juice ¹ indinavir itraconazole ketoconazole lopinavir/ritonavir nefazodone nelfinavir posaconazole ritonavir saquinavir telaprevir telithromycin voriconazole	amprenavir aprepitant atazanavir ciprofloxacin darunavir/ritonavir diltiazem erythromycin fluconazole fosamprenavir grapefruit juice ¹ imatinib verapamil

CYP Enzymes	Dual Inhibitor (Contraindicated)	Dual Inhibitor (Use with Caution)
CYP3A4 & CYP2C8	clopidogrel verapamil teriflunomide	trimethoprim ticargrelor

CYP Enzyme	Strong Inducer (Contraindicated)
CYP3A4	avasimibe carbamazepine phenytoin rifampin St. John's Wort

¹ The effects of grapefruit juice vary widely among brands, thus can be classified as both a strong and moderate inhibitor depending on concentration, quantity consumed, and preparation. Patients should be advised to avoid.

<http://www.fda.gov/Drugs/DevelopmentApprovalProcess/DevelopmentResources/DrugInteractionsLabeling/ucm093664.htm#classInhibit>

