8 PRIOR AND CONCOMITANT THERAPIES

8.1.1 Permitted Concomitant Medication and Medications that Should be Used with Caution

All concomitant medications will be recorded in the eCRF. The following concomitant medications are permitted during the study or should be used with caution:

- Lucitanib is highly bound to plasma proteins; therefore, use caution with warfarin, which is also highly bound to plasma protein and has a narrow therapeutic window
- Supportive care (e.g., antiemetics, analgesics for pain control) may be used at the investigator's discretion and in accordance with institutional procedures
- Drugs with possible risk to cause prolonged QT interval and/or possible risk or conditional risk to cause Torsades de Pointes must be used with caution (see [Appendix C](#))
- Transfusion of blood and blood products
- Treatment with antibiotics, anti-emetics, anti-diarrheals, analgesics, thyroid replacement therapy
- Bisphosphonates and denosumab in patients with bone metastases and for which the treatment was initiated prior to the initiation of study drug Considering the risk of drug-drug interactions, concomitant use of moderate inhibitors of CYP2C8 or CYP3A4 are not recommended during the study (see [Appendix E](#))
- Any other medication as appropriate, except for prohibited medications as described in [Section 8.1.2](#) below

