8.1.2 Prohibited Concomitant Medications

The following concomitant medications are not permitted during the study:

- Systemic anticancer therapy (e.g., hormonal therapy, immune therapy, targeted therapy), except for bisphosphonates and denosumab in patients with bone metastases
- Prior treatment with bevacizumab within 3 months prior to the first dose of lucitanib
- Radiotherapy during the treatment period is prohibited. Palliative bone radiotherapy at focal sites can be allowed during the screening period, before lucitanib intake and providing recovery is achieved before study drug initiation
- Drugs known to cause prolonged QT interval and/or know risk of causing Torsades de Pointes (see [Appendix C](#))
- Strong inhibitors of CYP2C8 or CYP3A4 are contraindicated during the study. Should acute treatment with a strong inhibitor be deemed necessary, lucitanib must be temporarily withheld. Lucitanib may be resumed after a minimum of seven days of ending acute treatment with a strong inhibitor of CYP2C8 or CYP3A4

- Co-administration of strong inducers of CYP3A4 ([Appendix E](#)) are not permitted at any time during treatment with lucitanib

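### Appendix E gives verapamil and teriflunomide two conflicting statuses, and the inhibitor ban in Section 8.1.2 names none of the three dual inhibitors that the appendix contraindicates

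*Protocol*

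**What the plan says.** Protocol Appendix E has one table for single-enzyme inhibitors, one for dual inhibitors of CYP3A4 and CYP2C8, and one for strong CYP3A4 inducers.

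- In the single-enzyme table, the column "Moderate Inhibitor (Use with Caution" contains teriflunomide (for CYP2C8) and, at the end of the CYP3A4 list, "imatinib verapamil".
- In the dual table, the column "Dual Inhibitor (Contraindicated" contains "clopidogrel verapamil teriflunomide".
- The only footnote on listings concerns grapefruit juice, which it explains may fall in either strength class.

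The body text works by strength class. Section 8.1.1, headed "Permitted Concomitant Medication and Medications that Should be Used with Caution", says that "concomitant use of moderate inhibitors of CYP2C8 or CYP3A4 are not recommended during the study" and points to Appendix E; the synopsis says the same. Section 8.1.1 ends by allowing any other suitable medication unless Section 8.1.2 prohibits it.

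Section 8.1.2 states: "Strong inhibitors of CYP2C8 or CYP3A4 are contraindicated during the study". It continues: "Should acute treatment with a strong inhibitor be deemed necessary, lucitanib must be temporarily withheld", with a restart no sooner than seven days after the strong inhibitor ends. The synopsis repeats both rules. Exclusion criterion 11 (Section 6.3 and synopsis) likewise names strong inhibitors and strong CYP3A4 inducers, not dual inhibitors.

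**The concern.** One appendix should not give a drug two statuses without saying which applies. For verapamil and teriflunomide, the investigator who follows the cross-reference in 8.1.1 arrives at the caution column, while the next table says the drug is contraindicated.

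The body text does not settle it. Its inhibitor prohibition is confined to strong inhibitors, and none of the three contraindicated dual drugs is listed as strong. For these drugs the column heading in Appendix E is the only prohibition in the protocol, and the general permission in 8.1.1 cuts against it.

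What is at stake is consistent handling of a safety rule across some 30–40 sites. Section 3.5.2 attributes lucitanib's oxidative metabolism in vitro about half to CYP2C8 and half to CYP3A4, with conjugation also contributing. A drug that inhibits both enzymes therefore acts on both main oxidative routes, which makes a separate dual table sensible and its unclear standing worth correcting.

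**Working it through.** No arithmetic beyond counting applies; the check sets the listings against the body rules.

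**Entries in Appendix E**

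- Strong: 1 (CYP2C8) + 16 (CYP3A4) = 17.
- Moderate: 1 (CYP2C8) + 12 (CYP3A4) = 13.
- Dual: 3 contraindicated + 2 caution = 5.

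**The five dual inhibitors**

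| Drug | Single-enzyme listing | Dual listing | Body rule that reaches it |
|---|---|---|---|
| Clopidogrel | none | contraindicated | none by name or class; falls to the general permission in 8.1.1 |
| Verapamil | moderate, CYP3A4 (caution) | contraindicated | discouraged, as a moderate inhibitor (8.1.1, synopsis) |
| Teriflunomide | moderate, CYP2C8 (caution) | contraindicated | discouraged, as a moderate inhibitor (8.1.1, synopsis) |
| Trimethoprim | none | caution | none by name or class |
| Ticagrelor | none | caution | none by name or class |

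**Conflicting status.** Verapamil and teriflunomide carry both labels: 2 of 5. The other three dual drugs carry one label each. Across the appendix, three entries are listed under two statuses: grapefruit juice, which the footnote explains, and these two, which nothing explains.

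**Reach of the body prohibition.** The contraindicated dual drugs that are also among the 17 strong entries number 0 of 3. The inhibitor ban in 8.1.2 and the synopsis, and the hold and seven-day restart attached to it, therefore reach 0 of 3. The inhibitor item in 8.1.2 does not cite Appendix E, whereas the strong-inducer item does, so the dual table is not brought in by reference either.

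**Chain for clopidogrel.** Its status within Appendix E is clear. It is in neither the strong nor the moderate column, so 8.1.2 does not prohibit it as an inhibitor and 8.1.1 allows what 8.1.2 does not prohibit. The conflict here is between body and appendix.

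**Scope.** 8.1.2 also bars strong CYP3A4 inducers and drugs with known QT or Torsades risk. The statement that only strong agents are covered applies to its CYP-inhibitor rule, not to the whole section.

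**The case against.** The best defence is that the two tables answer different questions: one grades strength on a single enzyme, the other judges the combined effect on both. Given the roughly equal split in Section 3.5.2, the dual table is naturally read as the more specific and so the governing one. That is plausible, and the fix adopts it, but the protocol does not say it, and it leaves the gap between appendix and body text open.

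Several objections to a stronger reading do stand.

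- A reader might infer that a site could continue verapamil or teriflunomide in full compliance with Appendix E. The documents do not support that: such a site would be disregarding an express contraindication in the same appendix, and even the lenient listing is discouraged in 8.1.1 and the synopsis. The real gap is between discouraged and barred.
- A reader might infer that nothing tells a site to hold lucitanib if one of these drugs becomes necessary. A contraindication already implies that the two are not given together. What is unstated is mainly the restart interval, and 8.1.2 gives no restart interval for strong inducers or known-QT drugs either.
- A reader might infer that the seven-day interval should simply carry over. The documents give no elimination data for the three drugs, so they do not support that figure.
- A reader might link the conflict to the frequent hypertension in Section 3.6.1.3 and the preference for calcium channel blockers in 7.4.1. The protocol names only the class there and leaves the choice to the investigator, so the documents do not show how often the conflict would arise.

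**Conclusion.** The point holds as an inconsistency in an operative safety rule. Two of the five dual inhibitors have conflicting statuses in Appendix E with no rule of precedence, and the body text, read literally, prohibits none of the three that the appendix contraindicates.

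Its weight is moderate. The documents do not give the size of the interaction or the number of patients concerned. The point bears on conduct and safety only; a reader might look for an effect on the sample size or the PFS analysis, but neither depends on these lists.

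The remedy assumes that the stricter label is the intended one, which the documents do not state and the sponsor must confirm. The columns of Appendix E read as intact in the available text, so the double listing does not look like an artefact of extraction.

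**What to change.** 1. Once the sponsor confirms the intended label, add a note to Appendix E: *A drug listed in the dual-inhibitor table has the status given there, whatever its single-enzyme listing.* The single-enzyme grades can stay.
2. In the prohibition sentence of Section 8.1.2 and of the synopsis, add: *and dual CYP3A4/CYP2C8 inhibitors listed as contraindicated in Appendix E*.
3. Align exclusion criterion 11 in the same amendment. It now matches 8.1.2 in covering only strong inhibitors. Widening 8.1.2 alone would let a patient with a continuing need for clopidogrel pass criterion 11 and then be barred from taking it on study.
4. Leave the restart interval open until clinical pharmacology has advised. The hold follows from the contraindication; apply the seven days to these drugs only if the sponsor confirms that it is long enough, or state another interval.

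The drafting cost is one table note, one phrase in two places and a matching edit to criterion 11. As a protocol amendment it needs IEC/IRB approval and regulatory submission (Section 13.7), so it can travel with the next amendment. The downside is that up to three co-medications are explicitly barred, and a few patients who need one may have to switch or not be enrolled. Concomitant medications are already recorded in the eCRF, so data collection and analysis do not change.
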